9.1.4 Limitation of bias

In order to limit bias, the sensitivity and specificity analysis need to be performed on a population as homogenous as possible. To this end, only patients treated with brodalumab (Kyntheum®) will be enrolled. By doing so we will limit the bias due to different treatment profiles (schedule of drug administration....). However, Kyntheum® efficacy will not be assessed during the study.

9.1.5 Study Schedule

The enrolment period is expected to be 5 months. After the patient's individual treatment plan has been decided, he/she will be approached for informed consent to participate in the study and deliver data to use for national and pooled analysis.

Investigators are expected to enter data into the site specific part of the CRF at baseline and at any patient contact throughout the duration of the study. In order to complete and sign-off the CRF, a medical record may be used as source for historical data.

Visits will be according to local clinical practice and not decided in advance by the study protocol.

[figure not shown]
Relevant data from every visit within 52 weeks after baseline will be collected.

For analysis the following applies:

Visits that falls within week 12-16 weeks are proxy for visit at 3 months. If more than one visit within this period, the visit closest to week 16 will be used for analysis.

Visits that falls within week 48-56 weeks are proxy for visit at 12 months (52 weeks \pm 4) .If more than one visit within this period, the visit closest to week 52 will be used for analysis.

The study design is the following:

The study will enrol consecutive patients planned to receive Kyntheum® and fulfilling the eligibility criteria. The assignment of the patient to Kyntheum® must not be decided in advance by the trial protocol, but must fall within current practice, and the prescription shall be clearly separated from the decision to include the patient in the study. The visit schedule is defined by the standard of care as there is no extra mandatory visits related to the participation in the study. Patients must be informed about the study and asked for consent to use their data, and patients willing to participate be enrolled.

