THIS DOCUMENT CONTAINS TRADE SECRETS, AND/OR COMMERCIAL OR FINANCIAL INFORMATION, PRIVILEGED OR CONFIDENTIAL, DELIVERED IN CONFIDENCE AND RELIANCE THAT SUCH INFORMATION WILL NOT BE COPIED OR MADE AVAILABLE TO ANY THIRD PARTY WITHOUT THE WRITTEN CONSENT OF LEO PHARMA A/S

baseline. The therapeutic objective achievement is defined as “satisfied” or “very satisfied” response on 4 points Likert scale.

- Level of concordance between the satisfaction level in regard to the therapeutic objective set by the PSO-TARGET QoL Component grid and the DLQI at the 2nd follow-up visit (52 ± 4 weeks.).
- Research of predictive factors (among baseline characteristics) of the achievement of the main treatment goal.
- Percentage of agreement between the physician-reported and the patient-reported dimensions at the first follow-up visit.
- Rate of patients having changed objective at the 1st follow-up visit (12/ 16 weeks).
- Percentage of patients who have maintained at 52 ± 4 weeks the level of satisfaction achieved at the 1st follow-up visit.
- PASI Scores at baseline, at the 1st follow-up visit (12/ 16 weeks), at the 2nd follow-up visit (52 ± 4 weeks.).
- Level of accordance between PASI 90/100 and the satisfaction level in regard to the therapeutic objective set by the PSO-TARGET QoL Component grid.
- DLQI Scores at baseline, at the 1st follow-up visit (12/ 16 weeks), at the 2nd follow-up visit 52 ± 4 weeks.

Data sources

Patients' data will be collected at day 0, at the 1st follow-up visit (12/16weeks) and at the 2nd follow-up visit at 52 ± 4 weeks according to the physician's practice.

As a prospective study, the following data will be collected during the patient visit: disease history, concomitant treatments, previous anti psoriatic treatment and adverse events. In addition, the following study specific data will be collected: disease severity (PASI score), quality of life questionnaires (DLQI, PSO-TARGET component grid).

Study size

The main criterion is the sensitivity of the PSO-TARGET tool (percentage of patients who consider their target objective as being achieved after 12/16 weeks of treatment as defined by a “satisfied or very satisfied” response, assessed on a 4 points Likert scale, among patients with a DLQI total score of 0 or 1).

The sample size calculation is based on the following hypotheses :

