9.2 Setting

The study is planned to be conducted in approximatively 25 sites in 2 countries. Investigators will be clinical dermatologists. Each participating site is expected to include in average 5/6 patients. In case of slow recruitment in some sites, the other sites will be allowed to enrol up to 10 patients. Inclusion requires that Kyntheum® is prescribed in accordance with the approved terms of the marketing authorization in the country and that none of the stated contraindications apply.

Caution should be taken by the treating physician concerning any precautions, warnings and potential drug interactions stated in the product label.

Patients should be included in the study only once.

The study aims to involve sites and investigators that are representative for HCPs that prescribe biologics to patients suffering from *psoriasis vulgaris*. Sites can be hospital (university, private, public) dermatology departments, private dermatology clinics, and all sorts of general practices. Sites where patients are prescribed Kyntheum®, but for continuation of care are routinely referred to a different site without access to prescribe Kyntheum®, should not be selected for this study.

Information about the PSO-TARGET study should be given after the decision is made to treat the patient with Kyntheum®. It will be emphasized that the participation study will not condition the patient treatment and will not alter the visit schedule defined by the standard of care (3 and 12 months). After enrolment (i.e. signature of the Informed Consent Form), the physician will provide the patient with the QoL component grid along with the DLQI questionnaire. After having explained the purpose of the table in regards to the study, the physician shall give the patient enough time to reflect on which component is the most important for him/her without influencing him/her. Both questionnaires will be answered after this reflection period.

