9.3 Variables

The following data will be collected from the patients' medical records and reported on the CRF by the investigator.

Consent

- Unique Study subject number (ISO three letter Country Code, followed by site number within country and consecutive patient number within site)
- Date of Informed Consent (dd.MMM.yyyy)
- Date of first case report recording (dd.MMM.yyyy)

Demographics

- Month/Year of Birth (MMM.yyyy)
- Gender (Male/Female)
- Weight (kg)
- Height (cm)

Medical History

- Date of diagnosis of psoriasis (dd.MMM.yyyy)
- Location of Psoriasis (List: scalp, nail, body, joint involvement, genital or intimate psoriasis, other)
- Body Surface Area (xx%)
- Commonly associated comorbidities (List: cardiovascular diseases, diabetes, hypertension, depression, psoriasis arthritis, inflammatory bowel disease, other)
- Smoking habits (never, active with pack years, not active with pack years and years since stopped)
- Alcohol consumption (never, occasionally or regularly with number of days/week, number of drinks per day when alcohol is used)
- Prior psoriasis treatment and posology + reason for discontinuation of the last therapy administered
- Standard occupational category.

Psoriasis treatments during study period

THIS DOCUMENT CONTAINS TRADE SECRETS, AND/OR COMMERCIAL OR FINANCIAL INFORMATION, PRIVILEGED OR CONFIDENTIAL, DELIVERED IN CONFIDENCE AND RELIANCE THAT SUCH INFORMATION WILL NOT BE COPIED OR MADE AVAILABLE TO ANY THIRD PARTY WITHOUT THE WRITTEN CONSENT OF LEO PHARMA A/S

- Study treatment & co-medications (product name, formulation, dose, number of prescribed packages, package size)
- Date of treatment initiation
- Date of discontinuation (dd.MMM.yyyy)
- Reason for discontinuation (noncompliance, adverse event, requirement for alternative therapy, death, pregnancy, other)

Severity/effectiveness

- Psoriasis area and severity index (PASI)

Patient Reported Outcome

- Dermatology Life Quality Index (DLQI) score
- PSO-TARGET QoL component grid

The collected data are presented in the following flow chart of the study :

THIS DOCUMENT CONTAINS TRADE SECRETS, AND/OR COMMERCIAL OR FINANCIAL INFORMATION, PRIVILEGED OR CONFIDENTIAL, DELIVERED IN CONFIDENCE AND RELIANCE THAT SUCH INFORMATION WILL NOT BE COPIED OR MADE AVAILABLE TO ANY THIRD PARTY WITHOUT THE WRITTEN CONSENT OF LEO PHARMA A/S

Reporter	Data to be collected	Base-line Visit (Day 0)	3 months Visit (week 12-16)	12 months visit (week 48-56)
Investigator	Unique Study subject	X		

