LEO/CLINACT will ensure that the protocol and any amendments and the Patient Information Sheet/Informed Consent Form, Diary and Questionnaires are submitted to the relevant Independent Ethics Committees (IECs) and/or competent authorities and/or other national or regional authorities according to local requirements. According to applicable regulations, LEO, CLINACT will submit required documents to the IEC, such as:

- periodic updates on the progress of the study
- notification of the end-of-study
- a summary of the study results

LEO will keep a copy of all documents submitted and an updated list of all submission and approval dates of all documents submitted to the IEC and/or authorities and will provide the Site Responsible with a copy of this list. Copies of the documents will be distributed upon request.

None of the data planned to be collected are expected to have any psychological impact on the participants, and the questions posed will be presented in a non-judgmental, objective manner so that the impact on the patient's behaviour and honesty in data reporting is minimized. The nature of the collected data will not make it possible to track the patients without access to the participant lists and Consent Forms stored at the Study Site. The collection of this data is considered ethically justified, based on these precautions and the following considerations.

This study focuses on collecting data on the real-life experience of biologic treated psoriasis patients for up to 56 weeks.

It will be a challenge to keep patients motivated to contribute data to the study long-term, but psoriasis patients are generally very willing to share their experience with those lending non-judgmental ears to their experience.

The Site Study Responsible must give the patient oral and written information about the study in a form that the patient can understand, and obtain the patient's written consent before collection of identifiable patient information (hereinafter referred to as personal data). Before consenting, the patient must be given sufficient time to consider and to pose questions. Since the study is observational the consent only concerns the data collection per se and is not consent to any interventional procedure or treatment.

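### The data-collection sentence in Protocol 9.1.5 ends at week 52, but the last visit window, and the rest of the protocol, run to week 56

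*Protocol*

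**What the plan says.** Section 9.1.5 (Study Schedule) sets the collection rule: "Relevant data from every visit within 52 weeks after baseline will be collected". It then gives the analysis rule for the last visit: "Visits that falls within week 48-56 weeks are proxy for visit at 12 months", with 12 months written out as 52 weeks plus or minus 4. If several visits fall in the window, "the visit closest to week 52 will be used for analysis".

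Three other places give the timing of the last data collection:

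- Abstract, Data sources: patients' data are collected "at the 2nd follow-up visit at 52 ± 4 weeks according to the physician's practice".
- Section 9.3, flow chart: the last column is headed "12 months visit (week 48-56".
- Section 10: the study collects data on "biologic treated psoriasis patients for up to 56 weeks".

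The study does not fix visit dates. Section 9.2 says that participation "will not alter the visit schedule defined by the standard of care (3 and 12 months").

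**The concern.** The collection sentence and the analysis window cannot both hold as written. The window needs data up to week 56, while the sentence promises data only up to week 52. Within 9.1.5 the 48 to 56 range is presented as a rule for analysis, so the 52-week sentence is that section's only stated limit on what sites collect.

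The choice of the visit nearest week 52 also presupposes data on both sides of that week. Take a patient seen at weeks 48 and 53. The analysis rule selects week 53 (1 week away, against 4), but the collection sentence supplies only week 48.

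The results at stake are the week-52 secondary ones: concordance of the grid with the DLQI (9.8.3), and maintenance of the treatment goal and evolution of PASI and DLQI (9.8.5). The DLQI and the satisfaction rating are completed by the patient at the time, so medical records cannot recreate them later. Section 9.8.3 also rules out replacing missing data for the secondary performance endpoints. With about 25 sites in two countries, different cut-offs could be applied.

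**Working it through.** **Reproducing the window.** 52 − 4 = 48 and 52 + 4 = 56 weeks, as stated. In days, 48 × 7 = 336 and 56 × 7 = 392, so the window holds 392 − 336 + 1 = 57 days.

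**Placing the collection limit.** 52 × 7 = day 364. Window days after the limit: 392 − 364 = 28. Share uncovered: 28/57 = 49%.

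**Other ways of counting.**

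- Limit at day 366 (12 calendar months in a leap year): 26/57 = 46%.
- All of week 52 inside, limit at day 370: 22/57 = 39%.
- Limit at day 364, window to the end of week 56 (day 398, 63 days): 34/63 = 54%.

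The uncovered part of the window is therefore between 39% and 54% of its days, and 49% on the plain reading. If the sentence ended at week 56, 0 of 57 days would be uncovered.

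**Share of visits.** The protocol gives no distribution of visit dates, so this part is assumption only. Take visit day as normal with mean μ and SD σ, truncated to the window, with a half-day correction. The share after day 364 is

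[Φ((392.5 − μ)/σ) − Φ((364.5 − μ)/σ)] / [Φ((392.5 − μ)/σ) − Φ((335.5 − μ)/σ)].

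| Mean day | SD 7 days | SD 14 days |
|---|---|---|
| 350 | 2.0% | 17.6% |
| 358 | 17.7% | 33.5% |
| 364 | 47.2% | 48.5% |
| 365 | 52.8% | 51.1% |
| 372 | 85.8% | 68.4% |

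The result runs from 2% to 86%, so no single share of visits can be quoted.

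**Timeline.** If enrolment starts on the last day of Q3 2020 and lasts the planned 5 months, the last patient enters at the end of February 2021. Adding 392 days gives late March 2022, before the Q2 2022 end of data collection. Collection to week 56 fits the milestones.

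**The case against.** The strongest reply is that no site would be misled. The sentence promises data from visits up to week 52. It does not say that later visits are excluded. The flow chart, which tells sites what to collect and when, shows weeks 48 to 56, and section 9.1.5 also expects CRF entries at every patient contact during the study. The schedule figure beside the sentence is not reproduced in the text available, so what it tells sites cannot be checked. Most of this stands: the protocol as a whole intends collection to week 56. It does not remove the contradiction within 9.1.5.

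A reader might also infer four stronger points, none of which the document supports.

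- **That data collection stops at week 52.** Only one sentence says so, and the abstract, flow chart and section 10 go further.
- **That half of the 12-month visits, or some 67 of 134 patients (134 × 0.5), would be lost.** The 49% is a share of days, not visits. The 134 are patients evaluable at week 12/16, before later attrition. The count also needs every site to take the restrictive reading, and no affected patient to have another visit in weeks 48 to 52.
- **That a visit at exactly 12 months is excluded.** On calendar days, 365 exceeds 364 by one. But 9.1.5 itself equates 12 months with 52 weeks, and a visit at week 52 is inside the rule.
- **That the adverse event table would mix observation periods.** Section 11.2 requires events to be reported within 24 hours of awareness, for current and past Kyntheum patients, whatever the visit window.

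**Conclusion.** The point holds as an internal inconsistency that should be corrected. The collection sentence in 9.1.5 leaves 28 of the 57 days (49%) of the protocol's own last visit window uncovered, while four places (the window itself, the abstract, the flow chart and section 10) extend to week 56. The 49% rests on counting day 364 as the limit and days 336 to 392 as the window; other counts give 39% to 54%.

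Any loss of data depends on sites applying the sentence literally and on visit timing, which the protocol does not state. It would be confined to the week-52 secondary endpoints. The week 12/16 primary endpoint, the sample size and adverse event reporting are untouched.

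**What to change.** In section 9.1.5, change 52 to 56 in the collection sentence, so that it covers every visit up to 56 weeks after baseline and agrees with the 48 to 56 window, the Data sources text, the flow chart and section 10.

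Make no change to the adverse event observation period. Ending it at the second follow-up visit or week 56, whichever came first, would give patients unequal observation of 48 to 56 weeks. As a general end to observation, it could also conflict with the rule that selects the visit nearest week 52.

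The cost is one number in one sentence. It adds no visit, questionnaire or analysis, and the planned milestones accommodate it.

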9.4 Data Source

Investigator will complete the CRF with assessments and information according to the protocol. In addition, participants (patients) will be asked to enter data about their psoriasis symptoms and their Quality of Life, during the data collection period.

The below described scores will be mandatory:

Psoriasis Area and Severity Index (PASI) is the most widely used tool for the measurement of severity of psoriasis in clinical research. PASI combines the assessment of the severity of lesions and the area affected into a single absolute score in the range 0 (no disease) to 72 (maximal disease).

The **Dermatology Quality of Life Index (DLQI)** is well recognized Quality of Life questionnaire in psoriasis and capture a combination of symptoms, impact on daily routines, and feeling of stigmatization. It is a simple 10-question validated questionnaire that has been used in over 40 different skin conditions in over 80 countries and is available in over 90 languages. Its use has been described in over 1000 publications including many multinational studies. It is recommended to provide indirect measure of disease severity and is well used in studies on psoriasis and mentioned in the UK-treatment guideline (for details, see section 9.1.3).

The **PSO-TARGET QoL component grid** is a novel tool designed using a retrospective survey based on the recollection and experience from 3 clinical dermatologists of patient's expectations. It contains 12 therapeutic goals equally distributed into the 4 major psychometric components classically used in quality of life studies in patients suffering from chronic diseases (Chassany, 2003; Forestier et al., 2019). These four dimensions are: physical, subjective, relational/social and therapeutic. It has never been used before since it was designed for the PSO-TARGET study. Each patient will be required to pick only one item in the grid as his/her main therapeutic goal (see section 9.1.2). Treatment satisfaction in regards to the chosen component will be assessed at 12/16 weeks and 52 weeks by a 4 points Likert Scale and the level of concordance will be compared to DLQI scoring classes (described in section 9.1.2).

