9.8.4 Efficacy analysis

- Secondary objective/endpoint : achievement of target objective at 12 weeks, per component

Evaluation at week 12/16 of the level of achievement of the main treatment goal identified by the patient in the table at baseline. This evaluation will be performed using a Likert scale in 4 points (“very satisfied”, “satisfied”, “unsatisfied”, “very unsatisfied”).

The achievement of the main treatment goal will be defined as a “satisfied or very satisfied” response.

It will be described on the efficacy population.

- The proportion of patients with achievement of the main treatment goal will be described and the confidence interval at 95% will be provided.
- The primary analysis will be performed with considering missing data as non responder, and a sensitivity analysis will be performed on patients without missing data (observed case).
- Search for predictive factors of efficacy.

The predictive factors of the achievement of the main treatment goal on completed patients will be searched among baseline characteristics using binary logistic regressions models. Univariate analyses will be used to select ($p\text{-value} \leq 0.20$) the explanatory variables to include

in the multivariate model. The results of univariate and multivariate analyses will be interpreted in terms of odds-ratios with their 95% confidence intervals

In case of correlated variables, only the more significant in univariate will be include in the multivariate model.

Variables with a rate of missing data $\geq 20\%$, or those with empty categories or with very small number will not be considered eligible for this research of predictive factors.

As part of one of the secondary objectives, the analyses performed for the efficacy endpoint are summarized in the table below :

Objective	Statistical analysis	Exposure measure	Outcome measure	Covariables
2.a	Proportions	N/A	Achievement of the main goal (yes /no) at 12/16 weeks	N/A
2.b	Proportions – sensitivity analysis	N/A	Achievement of the main goal (yes /no) at 12/16 weeks	N/A
2.c	Binary logistic regression models,	N/A	Achievement of the main goal (yes /no) at 12/16 weeks	Relevant confounders (eg : demographic data, medical history, previous treatment...)
2.d	Proportions	N/A	Achievement of the main goal (yes /no) at 12/16 weeks for each component	N/A

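### The visit-selection rule in Section 9.1.5 goes by date alone, so an in-window visit without questionnaires can displace one with a valid rating and DLQI (minor)

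*Protocol*

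**What the plan says.** Section 9.1.5 leaves visit timing to routine care: "Visits will be according to local clinical practice and not decided in advance by the study protocol". Investigators enter CRF data "at baseline and at any patient contact throughout the duration of the study", and "Relevant data from every visit within 52 weeks after baseline will be collected". For analysis, a visit in weeks 12 to 16 stands for the 3-month visit and one in weeks 48 to 56 for the 12-month visit. With several visits in the first window, the rule is "If more than one visit within this period, the visit closest to week 16 will be used for analysis"; in the second, "the visit closest to week 52 will be used for analysis". No other condition is attached.

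Section 9.2 says that participation "will not alter the visit schedule defined by the standard of care (3 and 12 months"). The flow chart in Section 9.3 has a single 3-month column in which the DLQI and the grid are marked. Section 9.4 introduces PASI, DLQI and grid with "The below described scores will be mandatory".

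The primary analysis (Section 9.8.3) cross-classifies the rating against the DLQI at week 12/16. Section 9.8.4 covers the secondary endpoint of goal achievement and states "The primary analysis will be performed with considering missing data as non responder", with an observed-case sensitivity analysis.

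**The concern.** The primary table needs two measures from the same patient at the same time point. The rule picks a visit before asking whether either measure exists there, and it offers no way back to another in-window visit.

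Week 16 is the upper edge of its window, so closest to week 16 always means the latest in-window visit. Routine care puts the visit at about week 13. If that patient is seen again in week 15 and no questionnaires are completed then, the rule selects week 15. A valid pair that is already in the database is set aside, with no analytic gain. The week 52 rule has the same gap, except that the displaced visit may be earlier or later than the selected one.

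At stake are evaluable patients in the primary table and, for the secondary achievement endpoint, satisfied answers turned into failures.

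**Working it through.** **1. The plan's own figure.** Inputs from Section 9.5: sensitivity 0.80 under the null and 0.90 under the alternative, alpha 0.05, power 80%, prevalence of DLQI 0-1 of 80%, 10% not evaluable. Section 9.8 makes tests two-tailed, so the upper tail is 0.025. The smallest group giving at least 80% exact binomial power is n1 = 107: reject at 94 or more successes, tail 0.0233, power 0.819. Then 107 / 0.80 = 133.75, rounded up to 134. Next, 134 / 0.90 = 148.9, rounded up to 149, which the plan states as 150. A one-sided 0.05 test would need n1 = 82, hence 103 patients, which does not match. The plan's figure is therefore reproduced on the two-sided test, and the visit rule enters none of these steps.

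**2. What the rule does with two in-window visits (weeks 13 and 15).**

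| Week 13 | Week 15 | Visit selected | Result |
|---|---|---|---|
| both measures | both measures | week 15 | ordinary prespecified tie-break, no loss |
| both measures | rating only | week 15 | no cell in the primary table; achievement scored from week 15 |
| both measures | DLQI only, or neither | week 15 | no cell in the primary table; non-responder in the secondary achievement analysis |
| neither | both measures | week 15 | no loss |

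Only the second and third rows do harm, and in both a usable pair exists.

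**3. Primary endpoint.** Sensitivity is TP / (TP + FN) and specificity is TN / (FP + TN). A patient without a rating or without a DLQI belongs to none of the four cells. The patient leaves the calculation and is not counted as FN or TN.

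**4. Room in the sample size.** 150 less 10% leaves 135 evaluable, one above the 134 needed. The protocol does not say how many patients would have two in-window visits, or questionnaires at only one of them. As pure illustration, if k further patients were lost beyond the 10% allowance, with 80% of those remaining at DLQI 0-1:

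| k | evaluable | n1 | exact power |
|---|---|---|---|
| 0 | 135 | 108 | 81.0% |
| 5 | 130 | 104 | 76.1% |
| 10 | 125 | 100 | 70.3% |
| 15 | 120 | 96 | 75.0% |

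The sequence is not monotone because exact binomial power is saw-toothed: n1 = 107 gives 81.9%, 106 gives 74.0% and 101 gives 79.2%. No cost in power per lost patient can be read from it.

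**5. Secondary achievement endpoint.** With up to 150 patients in the denominator, each satisfied answer replaced by a non-response lowers the rate by 1/150 = 0.67 percentage points. An affected patient whose displaced answer was unsatisfied changes nothing. If a share m of patients were affected regardless of their answer, an achievement rate A would become A(1 - m): a relative loss of 5% at m = 5% and of 10% at m = 10%. Both values of m are assumptions; the protocol supports neither. The observed-case analysis drops such a patient from numerator and denominator and does not bring the earlier answer back.

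**The case against.** The strongest reply is that the harmful case may hardly occur. Any visit in weeks 12 to 16 is by definition a 3-month visit, the flow chart marks the DLQI and the grid there, and the scores are mandatory. A second in-window visit should then carry both questionnaires too, and the rule becomes a normal tie-break. A reader might infer from the single flow-chart column that the questionnaires are completed only once in the window, but the chart sets no such limit. CRF entry at any contact is also broader than the visits to which the selection rule applies. All of this stands, and it makes the case an exception of unknown frequency. It does not make it impossible: visits follow local practice, and Section 9.5 itself allows for 10% not evaluable.

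A second reply is that handling of incomplete visits belongs in the statistical analysis plan. That would hold if the protocol had left selection open. It states a rule under the analysis conventions instead, so a later completeness condition would change that rule, and Section 9.7 requires known deviations to be set out in a revised plan before data collection ends.

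Three stronger readings are tempting and not supported:

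- That the patient is scored a non-responder in the primary analysis. The imputation appears only in Section 9.8.4, where primary analysis means the main analysis of a secondary endpoint.
- That planned power falls by a definite amount. The share affected is unknown, such patients may already sit within the 10% allowance, and the power figures are saw-toothed.
- That the loss falls mainly on patients doing badly. This is plausible for extra visits but not documented. If it were so, fewer satisfied answers and fewer DLQI 0-1 patients would be lost than under proportional loss.

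**Conclusion.** The point holds in a limited form. As written, both selection rules can pass over a valid in-window pair when the visit nearest the target week is incomplete, and in that case they can only lose information. The cost per affected patient is one evaluable patient in the primary table and, if the lost rating was a satisfied one, at most 0.67 percentage points of the secondary achievement rate. The total cannot be computed from the protocol and is probably small. The 134 evaluable and 150 included patients, and the planned power, stand. This assumes the rule is applied literally and that a second in-window visit does not always come with both questionnaires. Severity is minor; the case for change is that the improvement is free.

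**What to change.** In Section 9.1.5, reword both selection sentences along these lines: if more than one visit falls in the window, use the visit closest to week 16 (week 52) at which both the satisfaction rating and the DLQI were completed, both taken from the same visit. Where no in-window visit has both, the present date rule can stand and the planned handling of missing data applies.

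The cost is one clause in each of two sentences. It adds no visits, questionnaires or patients and changes no stated figure. It should be settled before anyone looks at the ratings, so that the choice of visit cannot depend on the answers.
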